Staging of Superficial Esophageal Adenocarcinoma using Volumetric Laser Endomicroscopy

March 12, 2021

Principal Investigator:

[name].
Barrett's Esophagus Unit
Division of Gastroenterology and Hepatology
Mayo Clinic
[name]
Email: [contact]
[contact]

Research Preceptor:

[name] MD
[name] Professor of Gastroenterology
Barrett's Esophagus Unit
Division of Gastroenterology and Hepatology
Mayo Clinic
[name]
Email: [contact]
[contact]

A. Background, Innovation and Significance:

The prognosis and management of esophageal adenocarcinoma (EAC) is strongly associated with the stage of disease. Accurate staging is particularly important for superficial EAC given that T1a disease can be treated effectively with endoscopic therapy while T1b disease generally requires esophagectomy due to a higher risk of lymph node metastasis.¹ Our current practice relies on histologic assessment of endoscopic mucosal resection (EMR) specimens to determine depth of invasion. Endoscopic resection and in particular endoscopic submucosal dissection may place patients with T1b disease at an unnecessary risk. Complications such as bleeding have been reported in up to 33%, perforation in up to 5% and esophageal stenosis in up to 30% of patients undergoing resection.² Furthermore, up to 15% of patients who undergo EMR will eventually require surgery.² Volumetric laser endomicroscopy (VLE) is an imaging platform that uses infrared light to generate cross-sectional views of the human esophagus with microscopic resolution.³ VLE has been used to detect dysplasia associated with Barrett's esophagus (BE) but its use in cancer staging has not been previously explored.^{4, 5} We propose that VLE can accurately and comprehensively stage T1 EAC. The use of this technology may help select patients with invasive disease for esophagectomy while avoiding complications associated with endoscopic resection.

B. Specific Aims:

Accurate staging of superficial EAC (T1a vs. T1b) is critical in guiding treatment of early luminal cancer. We hypothesize that VLE can accurately and comprehensively stage T1 EAC. Thus the specific aims of this proposal are:

1. To correlate depth of cancer invasion measured using VLE to depth of invasion established by EMR (clinical gold-standard) in a retrospective cohort of T1 EAC patients.

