A recent advancement in the field of volumetric laser endomicroscopy (VLE) is the release of an FDA approved image enhancement software termed Intelligent real-time image segmentation (IRIS) (Nine Point Medical, Bedford, MA). IRIS highlights established VLE features using a color-graded scale superimposed over cross-sectional and reconstructed en-face views. VLE IRIS features include (1) surface hyper-reflectivity, a pink graded color scale at the epithelial surface that represents the degree of signal decay over depth (signal attenuation), (2) hypo-reflective structures (epithelial glands), filled by a solid blue color and (3) lack of layered architecture represented by an orange graded color bar at the external rim of the VLE image. Our VLE console was recently upgraded with the IRIS software package. Following the study methodology of this IRB protocol we plan to use IRIS to locate and delineate neoplastic regions prior to biopsy or resection. This is a continuum of our work using a previous offline version of IRIS to measure VLE signal attenuation to determine stage (T1a vs T1b) of early esophageal adenocarcinoma. (Endosc Int Open. 2019 Apr;7(4):E462-E470) The use of IRIS is meant to facilitate VLE interpretation and does not impact patient care. VLE scans will be reviewed with and without IRIS enhancement.

D. Research Strategy:

a. Rationale:

We propose that the use of an advanced endoscopic imaging technology designed to image the esophagus in cross-section at microscopic resolution can accurately predict depth of invasion in patients with T1 EAC. An advantage of cancer staging using VLE is that it could prevent unnecessary endoscopic resection and associated complications. This technology also provides comprehensive assessment of the esophagus as compared to the current standard of practice that relies on a discrete area chosen for endoscopic resection to determine depth of invasion.

[figure not shown]
b. Preliminary Data and Published Data:

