measuring distance (μm) from mucosal surface to deepest point of invasion. (**Figure 3**) The Paris classification suggests a cut-off of 500 μm to divide depth of submucosal invasion into superficial (sm1) and deep (sm2). This classification has been correlated to depth of invasion defined by layer involvement: (1) **T1a EAC**: tumor invasion into the lamina propria or muscularis mucosa and (2) **T1b EAC**: tumor invading into the submucosa.⁹

c. **Correlation of VLE Signal Attenuation to Depth of Cancer Invasion:** A validated computer algorithm will be used to quantify the degree of signal attenuation in the T1 EAC EMR specimen database identified above. VLE signal attenuation measurements will be correlated to depth of invasion as determined by histology (dB/ μm). Based on these measurements, a cutoff signal attenuation value will be established to distinguish between superficial and deep invasion.

II. Aim 2: Diagnostic performance of VLE in staging T1 EAC

Patient Selection:

a. Patients referred to our institution for management of BE and early neoplasia will be prospectively enrolled in this study. Inclusion criteria include patients with T1 EAC who are undergoing endoscopic evaluation including EMR.

Inclusion:

- Patient over the age of 18
- Patient undergoing an upper endoscopy with prior-biopsy confirmed Barrett's Esophagus.
- Ability to provide written, informed consent
- No significant esophagitis (LA grade <B, C, and D)

Figure 4: Study flow diagram

Exclusion:

- Patients who have achieved complete remission of intestinal metaplasia (CR-IM)
- Patients without visible BE at the time of study EGD
- Patients for whom use of the NvisionVLE device would be in conflict with the instruction for use.
- Prior esophageal or gastric surgical resection
- Significant esophageal stricture requiring dilatation
- Patients who require anticoagulation for who biopsy would be contraindicated
- Patients who are known to be pregnant

b. Endoscopic Evaluation: Patients will undergo high-definition white light endoscopy/narrow band imaging with detailed inspection of the BE mucosa. The length of the BE segment will be measured using Prague criteria (circumferential length, maximal length). Area(s) of mucosal nodularity/irregularity will be classified (Paris classification) and their location recorded (o'clock position, distance from incisors). If clinically indicated, an area(s) will be chosen for EMR.

Figure4:Studyflow diagram

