d. Volumetric Laser Endomicroscopy: A VLE

Figure 4: Study flow diagram scan will be performed. The VLE scan will be systematically reviewed based on a previously established protocol. If an area(s) is chosen for EMR during

endoscopic evaluation it will be identified and demarcated using VLE laser markings. If additional areas of concern are identified under VLE, they will be demarcated using VLE laser marking. All area(s) demarcated with VLE but not identified on endoscopic evaluation will undergo targeted biopsies. Area(s) identified under endoscopic evaluation and demarcated with VLE will undergo EMR as outlined below. Standard surveillance biopsies will be obtained across the remaining BE segment.

e. Assessment of Cancer Depth of Invasion: VLE scans will be analyzed using an automated computer algorithm to measure degree of signal attenuation over areas demarcated for EMR. The signal attenuation cut-off established from *aim1* will be used to classify cancers as superficial vs. deep. EMR specimens will be reviewed for grade of tumor differentiation, depth of invasion, and presence or absence of lymphovascular invasion. Depth of tumor invasion will be measured as outlined above and used to classify cancers as superficial vs. deep.

f. Statistical Considerations and Data Analysis: This is a prospective cohort pilot study to determine the diagnostic performance of VLE in staging T1 EAC. To achieve a specificity of 90% with a 95% confidence interval, we estimate that a total of 60 patients with T1 EAC will need to be enrolled in this study taking into account that approximately 75% of patients will be staged as having T1a disease on histology. Sensitivity, specificity, negative predictive value, positive predictive value and diagnostic accuracy will be calculated for VLE compared to histology as the gold-standard in staging T1 EAC. Kappa statistics will be performed to test for agreement of the diagnostic methods.

Anticipated Results, Interpretation and Potential Pitfalls:

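### Does leaving areas seen only on VLE out of the Aim 2 accuracy analysis call for a change to the plan?

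*Combined protocol and SAP*

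**What the plan says.** All references are to the Combined protocol and SAP.

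- **Section B, Specific Aims**, gives the hypothesis, "We hypothesize that VLE can accurately and comprehensively stage T1 EAC", and leads from it to the aims with "Thus the specific aims of this proposal are". Aim 2 itself is narrower: the diagnostic performance of VLE in staging T1 EAC in a prospective cohort.
- **Section D.a, Rationale**, says that the technology "provides comprehensive assessment of the esophagus as compared to the current standard of practice that relies on a discrete area chosen for endoscopic resection". **Section C, Technology Review**, adds "we plan to use IRIS to locate and delineate neoplastic regions prior to biopsy or resection".
- **Aim 2, paragraph b**, has the resection areas picked during white-light and narrow-band inspection: "If clinically indicated, an area(s) will be chosen for EMR".
- **Aim 2, paragraph d**, separates the two kinds of area. Those chosen at endoscopy are laser-marked and resected. For the others, "All area(s) demarcated with VLE but not identified on endoscopic evaluation will undergo targeted biopsies". Routine surveillance biopsies are taken from the rest of the Barrett's segment.
- **Aim 2, paragraph e**, has the algorithm "measure degree of signal attenuation over areas demarcated for EMR", applies the Aim 1 cut-off, and reads depth of invasion on the EMR specimens.
- **Aim 2, paragraph f**, lists sensitivity, specificity, both predictive values, accuracy and kappa against histology. It names no separate analysis of VLE-only areas.

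**The concern.** The rationale presents reliance on one endoscopically chosen area as the weakness of current practice. Aim 2 then evaluates VLE on exactly such areas. The areas that VLE alone picks out, where any comprehensive view would show itself, are marked and sampled but drop out of the listed analysis.

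Two things seem to be at stake. First, a good Aim 2 result could be reported as support for comprehensive staging, when it shows only that VLE can sort endoscopically selected lesions into superficial and deep. Second, scans and biopsies of VLE-only areas will be in hand, yet paragraph f does not promise even a count of the patients who had them.

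**Working it through.** **1. Which areas can enter an accuracy table.** An area needs an index-test class and a reference depth.

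| Area | Attenuation class | Depth reference | Enters the table |
|---|---|---|---|
| Chosen at endoscopy, resected | yes (para. e) | yes, EMR specimen (para. e) | yes |
| VLE only, biopsied | none planned | none planned | no |

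Giving the second row an attenuation class would not admit it, because the reference depth would still be missing.

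**2. Whether the restriction biases the planned estimates.** Partial verification distorts sensitivity and specificity when the index result decides who gets the reference test. Here the resection areas are chosen at endoscopy (para. b), before the VLE scan (para. d), and the attenuation class plays no part in the choice. For endoscopically selected areas the estimates are therefore not distorted by this route.

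**3. Whether the sample size is affected.** Paragraph f gives 60 patients, 90% specificity, a 95% confidence interval and about 75% T1a. That is 60 × 0.75 = 45 T1a and 60 − 45 = 15 T1b. The interval half-width is not stated. At n = 45 the Wald half-width is 1.96 × √(0.9 × 0.1 / 45) = 0.088, and an assumed half-width of 0.0877 gives back 45 / 0.75 = 60. The patients are counted by histological stage, so leaving out VLE-only areas removes none of them.

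**4. How far scope could matter (assumptions only).** Suppose sensitivity is 0.90 in endoscopically selected deep lesions, a share f of all deep lesions is seen only on VLE, and sensitivity there is s. Sensitivity over all lesions is 0.9(1 − f) + s·f.

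- f = 0.10: 0.81 at s = 0, up to 0.90 at s = 0.9.
- f = 0.20: 0.72 at s = 0, up to 0.90 at s = 0.9.

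The documents give neither f nor s. Without a depth reference in those areas, no analysis of the planned data can estimate s.

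**5. What an added table could show.** Exact (Clopper-Pearson) 95% limits for x out of n are the 0.025 quantile of Beta(x, n − x + 1) and the 0.975 quantile of Beta(x + 1, n − x). The counts, and a biopsy yield of one third, are assumed.

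| Patients with a VLE-only area | 95% CI | Biopsy positive | 95% CI |
|---|---|---|---|
| 6/60 = 10% | 3.8% to 20.5% | 2/6 | 4.3% to 77.7% |
| 12/60 = 20% | 10.8% to 32.3% | 4/12 | 9.9% to 65.1% |
| 30/60 = 50% | 36.8% to 63.2% | 10/30 | 17.3% to 52.8% |

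Frequency would be estimated usefully. Yield would not, unless such areas are common.

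**6. Whether that table would test comprehensive staging.** It would not, for three reasons.

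- Finding neoplasia on biopsy measures detection, whereas Aim 2 concerns depth.
- Aim 1 will "quantify the degree of signal attenuation in the T1 EAC EMR specimen database identified above", so its cut-off separates superficial from deep invasion among cancers. It is not built to separate neoplasia from its absence, and crossing that class with a biopsy result does not assess staging.
- VLE-only areas are all areas that VLE flagged. Completeness also depends on neoplasia that VLE missed, which would come from the surveillance biopsies of the remaining segment.

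**The case for a change.** The strongest case for a change is that the aims are derived from a hypothesis containing the word *comprehensively*, that the rationale gives the word a definite meaning, and that the only data bearing on it have no listed analysis. One limiting sentence and a descriptive table would cost almost nothing and need no added procedure. Nor can one say that histology in paragraph f already covers the biopsies, because paragraph e gives VLE-only areas no attenuation class to compare.

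The reading of the text stands, and so does the caution: Aim 2 results should not be presented as evidence of comprehensive staging. The need to amend the plan does not. The word appears in the background, hypothesis and rationale. It does not appear in Aim 2, in paragraph f, or in the section on anticipated results, which promises only to separate superficial from deep cancer against histology. Paragraph e, directly before the analysis paragraph, already says where attenuation is measured. Nothing in paragraph f prevents the usual description of how many patients had VLE-only areas and what their biopsies showed, and a pilot report would normally include it.

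**Conclusion.** No change is needed. The restriction to resected areas is the sound choice, because only there does the plan have a depth reference. Its effect on the planned estimates is nil: no area with a reference depth is lost, the attenuation class does not decide who is resected, and the 60 patients are unaffected. No numerical loss can be derived, since the documents give neither the frequency nor the biopsy yield of VLE-only areas. The ranges shown rest on assumed values.

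What remains concerns the wording of the eventual report. The accuracy figures describe lesions selected at endoscopy, and any tally of VLE-only areas describes detection, best read beside the yield of the surveillance biopsies. An analyst following paragraphs d to f would see this without an amendment.

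This conclusion rests on the text alone. The study flow figure is not shown, and the scan-review protocol cited in paragraph d is not part of the documents.

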Our group has performed extensive work aimed at understanding the VLE features associated with BE dysplasia. These features include effacement of layered architecture, atypical gland conformations and increased epithelial (surface) VLE signal intensity.^{4, 5} More recently we validated a computer algorithm that performs segmentation and reconstruction of a VLE scan into an en-face view with superimposed signal intensity profiles. (Figure 1) VLE signal decay is dependent upon several tissue optical characteristics.⁶ This algorithm can be applied to estimate the depth of invasion based on degree of signal attenuation. Figure 2 highlights an example of how depth of invasion can be correlated with VLE signal attenuation. We also reported on the use of this technology to detect subquamous esophageal adenocarcinoma.⁷

Our group has also performed work on histologic determinants of mortality for patients with T1 EAC and described that evidence of lymphovascular invasion and deep margin involvement are significantly associated with reduced overall survival.⁸ Ultimately, the data obtained from the present study will help determine if histologic features such as lymphovascular invasion can also be quantified with VLE.

c. Study Design:

I. Aim1: VLE to histology correlation of T1 EAC depth of invasion

Endoscopic Mucosal Resection Database: Our group has developed a platform for imaging EMR specimens using VLE.⁴ Patients with BE undergo endoscopic EMR after participating in informed consent (IRB).

[figure not shown]

Figure 2: (A) endoscopic mucosal resection specimen of patient with T1a EAC and imaged with (B) VLE (C) Depth of invasion estimated by signal attenuation decay at 340 μm.

ID:12-006665). The fresh EMR specimen is imaged with VLE and inked for orientation. Through an established pathology core lab protocol (Proc 053417.002) for sectioning of the EMR specimens we are able to obtain direct imaging-to- histology correlation Using this imaging platform we have imaged over 200 EMR specimens since 2012 of which 60 specimens were obtained from patients with T1 EAC (T1a EAC, N=45; T1b EAC, N=15).

b. **Histopathologic Review:** EMR histology will be reviewed systematically to assess grade of tumor differentiation, depth of invasion, and presence or absence of lymphovascular invasion. Depth of invasion will be manually quantified by

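### The histologic reference is worded as superficial vs. deep by micron depth, but the question is T1a vs. T1b by layer, and the visible text does not equate the two

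*Combined protocol and SAP*

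**What the plan says.** **The question.** Section A gives the clinical reason for the contrast: "T1a disease can be treated effectively with endoscopic therapy while T1b disease generally requires esophagectomy". Section B repeats it: "Accurate staging of superficial EAC (T1a vs. T1b) is critical in guiding treatment of early luminal cancer". Section C describes the group's earlier attenuation work as done "to determine stage (T1a vs T1b) of early esophageal adenocarcinoma". The Aim 1 specimen database is counted by stage ("T1a EAC, N=45; T1b EAC, N=15"). Aim 2 item f (Statistical Considerations) sizes the study on about 75% of patients being T1a on histology, and compares VLE with histology for staging.

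**The reference.** Aim 2 item e says: "Depth of tumor invasion will be measured as outlined above and used to classify cancers as superficial vs. deep". The measurement outlined above is in Aim 1 item b (Histopathologic Review): a distance in microns "from mucosal surface to deepest point of invasion". Aim 1 item c sets the attenuation cut-off to separate superficial from deep invasion, and Aim 2 item e applies that cut-off.

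**The link between them.** Item b cites a Paris cut-off of 500 μm, used "to divide depth of submucosal invasion into superficial (sm1) and deep (sm2"). It then says: "This classification has been correlated to depth of invasion defined by layer involvement", and defines T1a as invasion into the lamina propria or muscularis mucosa and T1b as invasion into the submucosa.

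**The concern.** T stage depends on which layer the tumor reaches. Distance from the surface is a different quantity, and two tumors at the same distance can lie in different layers. The protocol recognises part of this difficulty when it names duplicated muscularis mucosa as a problem for measuring absolute depth.

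The terms do not bridge the gap. Section B uses superficial EAC for T1a and T1b together, while item b uses superficial for sm1, a subset of T1b. Neither use makes superficial mean T1a. Reporting that a classification has been correlated with layer does not say how a case is to be classed.

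The split enters twice: it tunes the VLE cut-off in Aim 1 and scores VLE in Aim 2. If it is not the T1a/T1b boundary, test and reference share the same departure from T stage and Aim 2 could not reveal it. The accuracy figures would then be read as support for a treatment-relevant distinction that they did not measure.

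**Working it through.** **1. The passages side by side**

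| Place | Contrast | Basis |
|---|---|---|
| Sections A, B, C | T1a vs. T1b | stage |
| Aim 1 item b, layer definitions | T1a vs. T1b | layer |
| Aim 1 item b, Paris cut-off | sm1 vs. sm2 | 500 μm of submucosal invasion; both sides are T1b |
| Aim 1 item c | superficial vs. deep | no rule given |
| Aim 2 item e | superficial vs. deep | measured depth, no threshold given |
| Aim 2 item f | staging, 75% T1a | histologic stage |
| Anticipated Results | staging, then superficial vs. deep, for the same task | no rule given |

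**2. The plan's own figure**

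Item f gives N = 60 and 75% T1a, so 0.75 × 60 = 45 T1a and 15 T1b. At a specificity of 0.90 the 95% half-width on 45 cases is 1.96 × √(0.90 × 0.10 / 45) = 0.088. So 60 fits a half-width of about 9 points. The plan states no half-width, so 60 can be neither confirmed nor called wrong. The calculation does show that the planned specificity denominator is T1a by stage, which makes T1b the positive class by implication.

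**3. What each reading gives**

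*(i) Superficial = T1a, deep = T1b.* The denominators are 45 and 15, and there is no distortion.

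*(ii) The 500 μm submucosal cut.* T1a and sm1 would be superficial and sm2 deep. Let k of the 15 T1b cases be sm1. The superficial group is 45 + k and the deep group 15 − k. Assume that VLE is 90% sensitive and 90% specific by layer, and equally so in sm1 and sm2. Apparent specificity is (45 × 0.9 + k × 0.1) / (45 + k):

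| k (assumed) | superficial / deep | apparent specificity |
|---|---|---|
| 0 | 45 / 15 | 90.0% |
| 3 | 48 / 12 | 40.8 / 48 = 85.0% |
| 5 | 50 / 10 | 41.0 / 50 = 82.0% |
| 10 | 55 / 5 | 41.5 / 55 = 75.5% |

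*(iii) Some other distance from the surface.* Let a distance cut misplace a share a of the 45 T1a and a share b of the 15 T1b cases.

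- Test perfect on T stage, scored against distance: TP = 15(1 − b), FP = 15b, FN = 45a, TN = 45(1 − a). At a = b = 0.10 these are 13.5, 1.5, 4.5 and 40.5. Apparent sensitivity is 13.5/18 = 75%, specificity 40.5/42 = 96% and accuracy 54/60 = 90%. Chance agreement is (15 × 18 + 45 × 42)/3600 = 0.60, so kappa is (0.90 − 0.60)/0.40 = 0.75. With shares of 5% and 15%, sensitivity is 86% and 65%, and kappa 0.87 and 0.64.
- Test that reproduces the distance class perfectly: every apparent measure is 100%. At a = b = 0.10 its true sensitivity for T1b is 13.5/15 = 90%, its true specificity 40.5/45 = 90% and its true PPV 13.5/18 = 75%.

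All values of k, a and b are assumptions. The documents give neither the sm1/sm2 split nor a distribution of micron depth. These figures show that the error can run in either direction. They do not estimate what will happen in this study.

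**The case against.** The best case on the other side is that this is only loose wording. Item e points back to the Histopathologic Review, which holds the layer definitions as well as the micron measurement, and those definitions are the only ones there that divide all T1 cases into two classes. Item f describes its gold standard as one for staging. The anticipated-results section speaks first of staging accuracy and then of distinguishing superficial from deep cancer, plainly meaning one task. No surface-distance threshold is given, so a distance reference cannot be applied from the text as it stands. Figures 3 and 4 are not visible and might carry the rule.

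Much of this stands. T1a/T1b is probably what is intended, and the review cannot say that the complete plan lacks a rule. But no visible sentence equates the terms, and the one place that attaches a threshold to them puts both inside T1b. An investigator following item e with that definition would build a reference that is not T stage. The planned review by two pathologists addresses the quality of assessment and leaves the choice of classes open.

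A reader might infer that the study will score VLE against a distance class, or that its accuracy will be off by the amounts illustrated. The documents support neither: the misplacement shares come from no source in them, and under the layer reading the distortion is zero.

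**Conclusion.** The point holds as an inconsistency between the stated question and the wording of the reference in Aim 1 item c and Aim 2 item e. It should be fixed, with medium confidence. Its effect depends on a choice that the visible text leaves open. There is none if the classes are assigned by layer. If the 500 μm cut or another distance cut is used, the accuracy measures and kappa would be those of a different contrast, and the planned denominators of 45 and 15 would not in general apply. The size in that case cannot be estimated from the documents. The conclusion rests on the text alone and assumes that the unseen figures do not supply the mapping. It is no criticism of N = 60 and no finding that bias will occur.

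**What to change.** In Aim 1 item c and Aim 2 item e, state that the binary histologic reference for both aims is T1a vs. T1b by layer, as already defined in the Histopathologic Review, with T1b as the positive class. Derive the Aim 1 attenuation cut-off against that reference, and compute all Aim 2 accuracy measures and kappa against it. Keep micron depth from the surface as a continuous variable for the Aim 1 correlation; other descriptive uses need not be excluded. Settle the definition before Aim 2 results are read, so that it cannot be chosen after the fact.

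The cost is a few sentences. N stays at 60, and the Aim 1 database is already counted as 45 T1a and 15 T1b. Two costs remain. Assigning layers where the muscularis mucosa is duplicated is difficult and relies on the two-pathologist review already planned. If an attenuation cut-off has already been derived on some other split, which the text does not show, it would have to be derived again.
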